1.1.3 Estimand

The estimand of the primary objective is defined by the following 5 attributes:

- Treatment: Single dose of AT132
- Population: Male participants with ventilator-dependent XLMTM, as defined by the inclusion/exclusion criteria of the study
- Endpoint: Change from baseline in hours per day of ventilation support at Week 24
- Intercurrent events and their corresponding strategies: For study discontinuation due to death or due to lack of efficacy, a composite strategy will be adopted, where participants with the intercurrent event before Week 24 having missing observation(s) after the intercurrent event will have those missing observations(s) imputed by unfavorable values ([Appendix 2](#))
- Population level summary: Mean change from baseline, by AT132 dose level

The estimand framework described above will be applied to all relevant primary and secondary efficacy endpoints.

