4 STATISTICAL ANALYSES

4.1 General Considerations

The study is no longer able to address the stated objectives, hence the statistical analysis will provide descriptive summaries by treatment groups.

Continuous data will be summarized descriptively including the number of participants (n), mean, standard deviation (SD), median, minimum and maximum. Categorical data will be summarized by frequencies and percentages. Percentages by categories will be based on the number of participants with no missing data, i.e. the percentages for the non-missing categories will add up to 100%.

All data summarization and analyses will be performed using SAS® Version 9.4 or higher on Red Hat Enterprise Linux. Specifications for table, figures, and data listing formats can be found in the TLF specifications.

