Each item of the questionnaire is measured on a 5-point likert scale from – 0 (Never) to 4 (Almost always). The module is composed of 25 items comprising 3 dimensions:

- About My Neuromuscular Disease (17 items)
- Communication (3 items)
- About Our Family Resources (5 items)
- Total Scale Score

Higher scales/scores indicate lower problems.

Scores are derived in the following way:

- Step 1: Transform Score

- Items are reversed scored and linearly transformed to a 0-100 scale as follows: 0=100, 1=75, 2=50, 3=25, 4=0.
- Step 2: Calculate Scores by Dimensions x
 - If more than 50% of the items in the scale are missing, the scale scores should not be computed, $x \text{ Mean score} = \frac{\text{Sum of the items}}{\text{number of items answered}}$.
 - If more than 50% of the items in the scale are missing, the Scale Scores should not be computed.
 - If 50% or more items are completed: Impute the mean of the completed items in a scale.
- Total Score: Sum of all the items over the number of items answered on all the Scales.

Per protocol, the parent-report version of the questionnaire is supposed to be administered. In the case that the child-report version of the questionnaire is administered, the scoring algorithm will be adjusted accordingly.

Total scores and corresponding change from baseline will each be analyzed by MMRM at Week 24 as described above and summarized descriptively by dose level group and visit.

4.4.2.2.6 Number (%) of age-appropriate clinically relevant gross motor function milestones attained through Week 24

Protocol versions 1 to 4:

Bayley and motor milestone collection was intermittent and not required in versions 1 – 4 of the protocol, so data may be missing for some participants at some visits. In addition, the motor milestone eCRF was not added until version 5.0 of the protocol. As such, the Bayley III item (referenced in [Table 1](#)) corresponding to each motor milestone will be used for the analysis of the motor milestone data collected under protocol version 1 – 4. If the Bayley III result is not available for the visit, but the participant attended the visit, then their result will be included in the summary as “missing”.

Protocol versions 5+:

The motor developmental milestones listed in [Table 1](#) below will be derived in form of Yes (achieved) and No (not achieved).

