‡ Duration of sitting in the reference (WHO Multicenter Growth Reference Study) is not clearly defined, so the same age is used for the expected age of achievement for both independent sitting milestones.

The number and percentage of participants achieving each gross motor function milestone will be summarized descriptively by low dose and high dose group by visit week through Week 24. A similar summary will be provided for visits occurring after Week 24.

The denominator of the percentage calculation will only include the participants who attended the visit and are expected to achieve the particular milestone based on their age (i.e., if at the time of an assessment the child is at least the age indicated in [Table 1](#), then they will be considered eligible for the milestone and will be included in the denominator). A child’s eligibility will need to be uniquely determined for each assessment at each time-point.

The denominator values will be included in the table.

The percent of age-eligible milestones that each participant achieves at Week 24 will also be summarized as a continuous (percentage) by visit and via shift table as an ordinal variable, by number and percent of participants in each category (None, at least 1, >1 to half of the expected milestones, >50% to <100% all expected milestones, All expected milestones) at baseline and shift post-baseline.

Number of age-eligible milestones expected at Week 24 (denominator for the calculation for the participant at the visit) is determined based on the age of the participant at the visit and the corresponding number of milestones expected for that age. The numerator of the calculation for the participant at the visit is the number of milestones that they have achieved. The corresponding percentage will be converted to the relevant category. The number of participants falling into each category regardless of age will be summarized at each visit.

Each participant's timeline of achieving the motor milestones will also be presented graphically.

Any assessment done prior to the date of the participant signing Protocol V 5.0 informed consent is assumed to correspond to protocol V1.0 – 4.0 data.

4.4.2.2.7 Percentage of participants achieving full ventilator independence at Week 24

“Full ventilator independence” is defined as: the date of removal from ventilator field on the “Assessment of Ventilator Parameters” eCRF is not blank or “Is subject on a ventilator” = “No” on the same eCRF.

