5.2 Appendix 2 Unfavorable Values for Efficacy Estimand Imputation

Endpoint	Variable	Imputed value after ICE occurrence through Week 48
Primary	Hours of ventilation support	24 hours
Key Secondary	Achieving functionally independent sitting for at least 30 seconds	No (0)
Secondary	CHOP INTEND Total Score	0
	MIP	0
	Myotubularin expression	0
	ACEND total score	0
	PedsQL Scale	0
	PedsQL Summary Score	0
	Number of age-appropriate gross motor function milestones achieved	0
	Full ventilator independence achieved	No

ICE = intercurrent event

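### The by-visit milestone percentages count only children who attended, which conflicts with the SAP's own rule that death or lack-of-efficacy discontinuation scores as zero milestones

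*SAP*

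**What the plan says.** Four parts of the SAP bear on this.

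- **Estimand (SAP 1.1.3).** "For study discontinuation due to death or due to lack of efficacy, a composite strategy will be adopted" when the event falls before Week 24, with later missing observations replaced by unfavorable values. The scope is wide: "The estimand framework described above will be applied to all relevant primary and secondary efficacy endpoints".
- **Imputed values (SAP Appendix 2).** The variable "Number of age-appropriate gross motor function milestones achieved" is set to 0 after the event, through Week 48. "Achieving functionally independent sitting for at least 30 seconds" is set to No, and so is full ventilator independence.
- **Milestone table (SAP 4.4.2.2.6).** "The denominator of the percentage calculation will only include the participants who attended the visit" and are old enough for the milestone. On age, "A child’s eligibility will need to be uniquely determined for each assessment at each time-point". The same section plans a second summary: each child's percentage of expected milestones, as a continuous variable and as a shift table that has a None category.
- **General rule (SAP 4.1).** "Percentages by categories will be based on the number of participants with no missing data".

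SAP 4.4.2.2 names the FAS as the analysis set for the secondary endpoints. The FAS is every dosed child with at least one post-dose efficacy assessment.

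**The concern.** The estimand treats death and lack-of-efficacy discontinuation as failure. The per-milestone table takes the same children out. A programmer who follows SAP 4.4.2.2.6 literally never reaches the Appendix 2 value, because a child with no visit fails the attendance condition and has no assessment at which age eligibility could be judged.

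The resulting percentage answers a different question: how many of the children still alive and attending have the milestone. In a trial with fatal outcomes in both dose groups, that percentage can look better because children died. There is no hypothesis test behind these tables, so the descriptive percentages are themselves the result and will be read as success among treated children.

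**Working it through.** **The plan's own figure.** The SAP states no expected value for the milestone percentages. Its only design figure is N = 10 in SAP 4.9, for the abandoned comparison with control. A two-sided t-test at 0.05 with difference 13.0 and SD 6.0 has 72.4% power at 4 per arm and 85.0% at 5 per arm, so N = 10 reproduces. It has no bearing on this point.

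**Inputs**

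- High-dose group: 17 children at the 08 July 2020 cutoff (Protocol 1.4.2).
- Low-dose group: 7, an assumption. Protocol 1.4.2 gives 6. Protocol 3.1 has 3 controls still undosed, and SAP 1.3 excludes two controls as never dosed: 6 + 3 − 2 = 7. If all three had been dosed it would be 9, used here as the upper range.
- Deaths: 1 low dose and 3 high dose (Protocol 1.5). Timing relative to the visits is not given, so every count from 0 up to these is considered.
- Simplifications: every child is old enough for the milestone, every survivor attends, and there are no lack-of-efficacy discontinuations.

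**Formulas.** Let N be the children in the group, d the deaths before the visit (taken as before Week 24), and x the children with the milestone.

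- Attended-only percentage: x / (N − d)
- Percentage with Appendix 2 applied: x / N
- Ratio of the two: N / (N − d)
- Difference: x·d / [N(N − d)]. It is largest when every survivor has the milestone (x = N − d), where it equals d / N.

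**Results**

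| Group | d | Ratio | Largest difference |
|---|---|---|---|
| High, N = 17 | 0 | 1.00 | 0 |
| High, N = 17 | 1 | 17/16 = 1.06 | 1/17 = 5.9 points |
| High, N = 17 | 2 | 17/15 = 1.13 | 2/17 = 11.8 points |
| High, N = 17 | 3 | 17/14 = 1.21 | 3/17 = 17.6 points |
| Low, N = 7 | 0 | 1.00 | 0 |
| Low, N = 7 | 1 | 7/6 = 1.17 | 1/7 = 14.3 points |
| Low, N = 9 | 1 | 9/8 = 1.13 | 1/9 = 11.1 points |

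Mid-range examples: at high dose with 3 deaths and 7 achievers, 7/14 = 50.0% against 7/17 = 41.2%. At low dose with 1 death and 3 achievers, 3/6 = 50.0% against 3/7 = 42.9%.

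**Sitting and ventilator independence.** SAP 4.1 drops only missing values. A child given No under Appendix 2 is no longer missing and stays in the denominator as a failure, provided the imputation is done first. SAP 4.4.1 and 4.4.2.2.7 do not mention the imputation, and the order of the two steps is not stated.

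**The case against.** The best defence is that the conflict is confined to one table and is visible there. SAP 4.4.2.2.6 prints the denominators, survival is reported by dose on the FAS, and no hypothesis is tested. The per-child percentage of expected milestones carries no attendance rule, and an imputed 0 falls naturally into its None category. The SAP version history also records, for the key secondary endpoint, a deliberate move to describing only available results.

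Much of this stands, and it limits the consequence. It does not remove the conflict. A printed denominator shows that children are absent, not that the estimand counts them as failures, and a survival curve does not correct a milestone percentage. The version history also shows that Appendix 2 was edited in version 4.0 (one variable removed, the span set to Week 48) while the milestone row was kept, so the row is not leftover text.

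A reader might infer more than the documents support:

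- *That SAP 4.1 itself removes deaths from the sitting and ventilator-independence percentages.* It does not. Appendix 2 gives those children a value, and only the order of steps is unstated.
- *That both exclusions stack.* Take 7 low-dose children with one death, one child who attended but was not assessed, and four achievers. Applying both exclusions gives 4/5 = 80%. But under the milestone rule the unassessed child attended and stays, while for sitting the child who died stays as No and the unassessed child leaves. Each gives 4/6 = 67%.
- *That the distortion is known to differ by dose because early collection was incomplete.* The SAP does say "Bayley and motor milestone collection was intermittent and not required in versions 1" 1 to 4, and the first six low-dose children passed Week 24 before protocol v5. But Protocol 1.4.2 describes Week 24 biopsy results in the high-dose cohort as part of the v5 dose decision, so high-dose children also reached Week 24 around or before v5. No count of missing assessments by dose is given.
- *That the estimand calls for bounds with missing counted as achieved and as not achieved.* It covers only death and lack of efficacy, so such bounds would be a preference.

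**Conclusion.** The point holds for the per-milestone by-visit table. SAP 4.4.2.2.6 and the composite strategy of SAP 1.1.3 with Appendix 2 give different denominators for the same child, and the attendance rule overstates success relative to the SAP's own estimand. The overstatement is 0 to 17.6 percentage points at high dose and 0 to 14.3 at low dose (0 to 11.1 if that group has 9 children).

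The range starts at 0 because the timing of the deaths is not in the documents. Its upper end needs every reported death to precede the visit and every survivor to have the milestone. It also rests on the assumed low-dose size and on all children being old enough. For late milestones with fewer eligible children, the figure could move either way.

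For sitting and ventilator independence the gap is smaller: the SAP needs to state the order of imputation and the non-missing rule. The analysis is descriptive, so no error rate is affected. The change should be made before the tables are produced.

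**What to change.** In SAP 4.4.2.2.6, for visits through Week 48, keep every FAS child with the intercurrent event in the per-milestone denominator and count the milestone as not achieved. Where no visit took place, set eligibility by the age the child would have had on the scheduled visit day, and use the same age for the number of milestones expected. The attended-only table may stay as a supplementary display, labelled as such.

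In SAP 4.1 or Appendix 2, add one sentence saying that the Appendix 2 values are assigned before the non-missing rule is applied, so that these children remain in the sitting and ventilator-independence percentages as No. Show n/N and the number missing for each of these endpoints.

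The cost is a few sentences of SAP text and simple programming, with no new data collection. The downside is slightly lower reported percentages.

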Any motor milestone value that is collected prior to participants’ date of signing the informed consent for Protocol Version 5.0 will use the flowchart logic described in the “Protocol versions 1 to 4” section above for deriving the motor milestone achievement status. Records collected after that date will follow the logic corresponding to the “Protocol versions 5+” section.

Table 1 Motor Developmental Milestones

Development Milestone	Reference	Summary Description of Performance Criteria*	Expected Age of Achievement for Analysis (months)
Head Control	Bayley-III Gross Motor Subtest Item #9	Child holds head erect for at least 15 seconds without support	4.0†
Rolls from Back to Sides	Bayley-III Gross Motor Subtest Item #20	Child turns from back to both right and left sides	6.0†
Sits Without Support	WHO Multicentre Growth Reference Study	Child sits alone without support for at least 10 seconds	9.2^‡
Sits Without Support	Bayley-III Gross Motor Subtest Item #26	Child sits alone without support for at least 30 seconds	9.2^‡
Stands with Assistance	Bayley-III Gross Motor Subtest Item #33	Child supports own weight for at least 2 seconds	11.4^
Crawls	Bayley-III Gross Motor Subtest Item #34	Child makes forward progress of at least 5 feet by crawling on hands and knees	13.5^
Pulls to stand	Bayley-III Gross Motor Subtest Item #35	Child raises self to standing position using chair or other convenient object for support	12.0†
Walks with Assistance	Bayley-III Gross Motor Subtest Item #37	Child walks by making coordinated, alternating stepping movements. He/she may hold on with 1 or 2 hands for support.	13.7^
Stands Alone	Bayley-III Gross Motor Subtest Item #40	Child stands alone for at least 3 seconds after you release his or her hands.	16.9^
Walks Alone	Bayley-III Gross Motor Subtest Item #42	Child takes at least 3 steps without support, even if gait is stiff-legged and wobbly	17.6^

* See motor milestone manual for full description of performance criteria

† Per CDC. For the milestones covered by the CDC, the age at which >75% of children attained the milestone is used as the reference for analysis here.

^ Per WHO Multicenter Growth Reference Study (MGRS), 2006. For the milestones covered by the WHO MGRS, the upper bound of the range (1-99%) is used as the reference for analysis here.

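### The participant-level milestone score needs an age-limited numerator, exclusive categories, and one item set for every protocol version

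*SAP*

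**What the plan says.** SAP 4.4.2.2.6 introduces the participant-level score as "The percent of age-eligible milestones that each participant achieves at Week 24", and Appendix 2 names the variable "Number of age-appropriate gross motor function milestones achieved". The denominator is the number of Table 1 milestones expected at the child's age at the visit. For the other half of the fraction the SAP says: "The numerator of the calculation for the participant at the visit is the number of milestones that they have achieved".

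The percentage is summarized as a continuous variable and, in a shift table from baseline, in five categories: "None, at least 1, >1 to half of the expected milestones, >50% to <100% all expected milestones, All expected milestones". SAP 4.1 adds that, for categorical data, "the percentages for the non-missing categories will add up to 100" percent.

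Table 1 lists ten milestones. Nine refer to a Bayley-III gross motor item. The tenth, "Child sits alone without support for at least 10 seconds", refers to the WHO growth study and has no Bayley-III item. For earlier data the Bayley-III item "corresponding to each motor milestone will be used for the analysis of the motor milestone data collected under protocol version 1 – 4". The missing-data sentence begins "If the Bayley III result is not available for the visit, but the participant attended the visit, then their result will be included"; such a result is to be labelled as missing. From version 5.0 consent onward each milestone is derived as Yes or No.

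**The concern.** Three parts of the rule do not give the score that the section describes.

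1. **Numerator.** The sentence a programmer would code counts every milestone achieved, over a denominator that counts only those expected by age. A score can then pass 100%. Less visibly, a milestone reached early can stand in for an expected one that was missed.
2. **Categories.** A child with most or all expected milestones also has at least one. As worded, that child belongs in two rows, and the percentages cannot total 100.
3. **10-second sitting.** Before version 5.0 consent this item has no stated data source, yet age alone puts it in the denominator. The score then depends partly on which protocol version governed the visit, and version is related to dose group.

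No hypothesis test is at stake (SAP 2). What is at stake is whether a descriptive secondary table by dose can be reproduced, and whether its rows mean the same for each child.

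**Working it through.** The SAP states no figure for this score, so there is none to reproduce. The inputs are the Table 1 ages, in months: 4.0, 6.0, 9.2 (twice), 11.4, 12.0, 13.5, 13.7, 16.9 and 17.6.

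**Expected counts, and the pre-version 5.0 maximum.** The last column takes an age-limited numerator and a child who achieves every milestone that has a Bayley-III item: (expected − 1) / expected once 10-second sitting is expected.

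| Age from (months) | Expected | With a Bayley-III item | Maximum score |
|---|---|---|---|
| 4.0 | 1 | 1 | 100% |
| 6.0 | 2 | 2 | 100% |
| 9.2 | 4 | 3 | 75% |
| 11.4 | 5 | 4 | 80% |
| 12.0 | 6 | 5 | 83% |
| 13.5 | 7 | 6 | 86% |
| 13.7 | 8 | 7 | 87.5% |
| 16.9 | 9 | 8 | 89% |
| 17.6 | 10 | 9 | 90% |

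If the item were removed from both parts of the fraction, the same child would score 100% in every band. The treatment matters lower down too: two milestones at 9.2 months give 2/4 = 50% with the item kept and 2/3 = 67% with it removed, which is a different category.

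**Numerator (hypothetical children).** From 9.2 to under 11.4 months four milestones are expected. A child who has all four and also stands with assistance scores 5/4 = 125%, and no category covers that. From 13.7 to under 16.9 months eight are expected. A child who does not crawl, has the other seven, and already stands alone scores 8/8 = 100% by the numerator sentence but 7/8 = 87.5% by the lead-in. From 17.6 months all ten are expected, so the two readings agree. Day 168 is 168/30.44 = 5.5 months after dosing, so at Week 24 the difference concerns children dosed before about 17.6 − 5.5 = 12.1 months.

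**Categories.** Suppose at least 1 is read as exactly 1. The only overlap left is a child with one achieved of one expected (4.0 to under 6.0 months), who is in both the exactly-one and the all-expected rows.

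**No milestone expected.** Under 4.0 months the fraction is 0/0. At Day 168 every child is at least 5.5 months old, so this cannot occur there. It can occur at baseline, one axis of the shift table.

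**Who falls under the earlier rule.** Protocol 1.4.2 says that the six low-dose children were all at least 2 years past dosing at the 08 July 2020 cutoff, so they were dosed by 08 July 2018. Version 5.0 is dated 01 May 2019, at least 297 days later. The Week 24 milestone window ends at Day 210 (SAP Table 9), so all six Week 24 assessments precede version 5.0. SAP 4.3.1 places all Part 2 dosing under version 5 or later. Protocol 1.4.2 also cites Week 24 results in Cohort 2 when the dose was chosen for version 5, so some Part 1 high-dose children share the earlier rule. 10-second sitting is in the Day 168 denominator for any child dosed at 9.2 − 5.5 = 3.7 months or older.

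**The case against.** Context answers much of points 1 and 2. The endpoint name, the section heading, the lead-in and Appendix 2 all carry the age restriction, and a top category of all expected milestones presupposes a numerator no larger than the denominator. The next label starts above one, so the category before it almost certainly means exactly one. Scores above 100% also look unlikely here: five of the six low-dose children could not sit for 30 seconds at baseline, and Part 2 excludes children who can. All of this stands. It makes points 1 and 2 corrections of wording rather than of intent. They are still needed, because the numerator sentence is the operative one and says something else.

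On point 3, a reader might infer that the SAP has no rule and the score is undefined. The text does not support that: the denominator is set by age alone and nothing permits dropping an item, so the literal result is that the item stays in uncredited. The criticism is of that result. The SAP also refers to flowchart logic for the earlier data. No flowchart is visible in the copy read, and a figure may have been lost; if it supplies a source or a rule for the item, point 3 falls.

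The same section also plans tables for each milestone with printed denominators, and a milestone timeline for each participant. A careful reader could therefore see past a distorted composite.

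**Conclusion.** The point holds as a defect of definition in a descriptive secondary endpoint.

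Points 1 and 2 rest on the text and are firm. The numerator sentence contradicts the section's own name for the score, with effect only before 17.6 months of age. The categories overlap as worded, and under the probable intended reading only the one-of-one case remains.

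Point 3 holds with moderate confidence, on the assumptions that the numerator is limited by age and that the unseen flowchart gives no source for the item. A child aged 9.2 months or older, assessed before version 5.0 consent, then cannot be classed as having all expected milestones and is capped at 75% to 90%. A child assessed later can reach 100%.

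A reader might go on to infer that the low-dose group is scored down relative to the high-dose group. The documents do not support a net direction or size. Some high-dose children fall under the same rule, and neither ages nor data availability are given. Nor do the documents show how many children, if any, would score above 100%.

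**What to change.** - **Numerator:** count only milestones in the child's age-expected set at that assessment.
- **Categories:** make them exclusive, for example 0; exactly 1 but not all expected; more than 1 and up to 50%; over 50% and under 100%; 100%. Set the score to not applicable when no milestone is yet expected.
- **Item set:** compute the composite on the nine Bayley-referenced milestones for all children and all protocol versions. The expected count is then 1 to 9, starting at 4.0, 6.0, 9.2, 11.4, 12.0, 13.5, 13.7, 16.9 and 17.6 months. Report 10-second sitting as its own row, marked as having no Bayley-III source before version 5.0 consent. At a minimum, take that item out of both numerator and denominator for assessments before that consent.
- **Flowchart:** include the one the section refers to, or delete the reference.

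The cost is a few sentences of SAP text and a small change to the derivation, with no new data. The downside of the nine-item composite is that valid 10-second sitting data from version 5.0 onward, on a milestone listed in the protocol, would appear only in the separate row.
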